1 PROTOCOL SUMMARY

1.1 Synopsis

[figure not shown]
Title:	The Theranostic Approach Towards Personalized Medicine Using Low Dose Y90 Microspheres for Radioembolization Therapeutic Planning (A Phase 2 Study)
Study Description:	Hepatocellular carcinoma (HCC) is the second deadliest cancer globally, with a 5-year survival of 18% in the and less than 20% of patients eligible for curative surgical treatment. Although Yttrium-90 (Y90) radioembolization (RE) is an established therapy in patients

	
with unresectable HCC, it has variable response due to many internal and external factors, including tumor histology and vascularity. A critical factor predicting tumor response (TR) is delivery of tumoricidal dose to targeted lesions. Optimizing individualized Y90 dosimetry will likely improve targeted TR and survival, while minimizing lung and liver toxicity. Technetium-99m macroaggregated albumin (^{99m}Tc-MAA) is currently used as the primary radiotracer for shunt studies prior to Y90 RE. However, ^{99m}Tc-MAA falls short in accurately predicting Y90 biodistribution in the liver and lung after RE. By evaluating the safety and efficacy of low dose Y90-microspheres as the radiotracer for pre-treatment shunt study, our goal is to address an unmet public health need by improving TR post-Y90 therapy through prospective personalized dosimetry. We hypothesize that using low dose Y90 microspheres as the treatment planning radiotracer will allow accurate prediction of therapeutic Y90 liver biodistribution, which will enable us to perform prospective personalized dosimetry for every individual patient. The results of this study will determine the safety and efficacy of using low dose Y90 as a direct surrogate for treatment planning to ensure delivering cytotoxic Y90 dose to the targeted tumor(s), while concomitantly minimizing liver and lung toxicity with more accurate prediction of therapeutic Y90 biodistribution. Our long-term objective is to increase the likelihood of objective tumor response, prolonged progression-free survival (PFS) and overall survival (OS) in patients with HCC treated with Y90 RE.

Objectives:	
Primary Objective: Compare the safety and accuracy/efficacy of low dose Y90 resin microspheres and MAA in predicting the actual dose delivered to the tumor, liver, and lung after Y90 therapy.
 
Secondary Objectives:
 
 1. Optimize low dose Y90 techniques in predicting TNR and LSF. 2. Identify tumor dose response thresholds (TDRT) and tumor dose distribution in patients with HCC treated with Y90 resin microspheres.
Endpoints:	
Primary Endpoint: The lung shunt fraction (LSF) and tumor to normal liver activity ration (TNR).
 
Secondary Endpoints:
 
 1. Monitoring all grades of Y90 related toxicity

	2. Tumor response evaluation at 1, 3 and 6 months and determination TDRT
Study Population:	N=30 patients with hepatocellular carcinoma (HCC), male or female, =>18 years of age, all ethnicities, ECOG <2, and generally local patients referred to Winship.
Phase:	2
Description of Sites/Facilities Enrolling Participants:	All patients will be recruited at Emory Interventional Radiology Clinics after they have been discussed and referred through multidisciplinary liver tumor boards. Only patients that are found to be ideal candidates for Y90 radioembolization at tumor boards will be considered for recruitment. Emory University Hospital and Emory University Hospital Midtown will be the clinical sites to perform the study.
Description of Study Intervention:	In this study, patients with HCC who are found to be ideal candidates for HCC and who would fit our inclusion criteria, described below, will be recruited. Patients will undergo standard of care mapping study with ⁹⁹ TC-MAA to plan for Y90 radioembolization therapy. The additional, non-standard of care, intervention will be to do a second mapping study using low-dose Y90 (15 mCi) before the therapeutic Y90 radioembolization. The distribution of MAA in terms of lung shunt fraction (LSF) and tumor to normal liver activity ratio (TNR) will be compared to that of low-dose Y90. The treatment planning will be performed using standard of care MAA biodistribution using partition dosimetry model. After administration of therapeutic Y90 dose, the actual dose delivered to tumor, non-tumoral liver (NTL) and lungs will be compared to the dose predicted by MAA and low-dose Y90. The patients will be followed-up clinically and with imaging at 1, 3 and 6 months to determine tumor response, potential treatment related toxicity and to determine TDRT.
Study Duration:	24 months
Participant Duration:	6 months

[figure not shown]
1.2 Schema

Overall Study Flow Chart

1.3 Schedule of Activities (SoA)

Study Flow Chart for Individual Patients

Estimated Timeline for Weeks 1-2 (Mapping and Treatment Week)

Monday:

7:30 AM-9:30 AM: 1st Angiographic study for mapping and MAA delivery

10:00 AM-11:00 AM: MAA SPECT/CT (Patient will go to nuclear medicine with radial/femoral arterial access sheath in place)

11:30 AM-1:00 PM: 2nd Angiographic study for low-dose Y90 delivery (After the procedure, patient's femoral sheath will be removed and hemostasis will be achieved with manual compression or closure device. If procedure performed via radial access, which is more commonly performed currently at Emory, the radial sheath will stay in and removed according to IR protocol after Y90 SPECT/CT.)

2:00 PM-3:00 PM: Y90 Bremsstrahlung SPECT/CT

3:00 PM-3:30 PM: Removal of the radial sheath at IR post procedural area and discharge.

4:30-5:30 PM: Y90 PET/CT.

Patient is free to go home after this.

Thursday:

11:00 AM-12:30 PM: 3rd angiographic study to deliver therapeutic dose of Y90.

1:00 PM-2:00 PM: Y90 Bremsstrahlung SPECT/CT (After the procedure, patient's femoral sheath will be removed and hemostasis will be achieved with manual compression or closure device. If procedure performed via radial access, which is more commonly performed currently at Emory, the radial sheath will stay in and removed according to IR protocol after Y90 SPECT/CT.)

3:00 PM-3:30 PM: Removal of the radial sheath at IR post procedural area and discharge.

4:30-5:30 PM: Y90 PET/CT.

Patient is free to go home after this.

Study Procedures	Screening Visit Week 0	Therapy planning/mapping Week 1-2	Y90 sirsphere treatment Week 1-2	1 week post procedure Week 6	1 month post procedure Week 6	3 months post-procedure Week 14	6 months post-procedure Week 26
Informed consent	X						
Entry Criteria	X						
Demographics	X						
Medical/surgical Hx	X						
Blood sampling	X				X	X	X
Collect list of medications	X						
Vital signs	X						
Physical exam	X						
Phone follow-up by [name] or Research Nurse				X			
MRI W & WO contrast	X				X	X	X
Conventional MAA angiography		X					
Low dose Y90 shunt study angiography		X					
SPECT/CT		X	X				
PET/CT		X	X				
Y90 Treatment			X				
Post Procedure Clinic follow up					X	X	X

2. INTRODUCTION

2.1 Study Rationale

Less than 20% of patients with HCC are eligible for curative surgical resection in the United States, with a 5-year survival of 18%[1]. Y90 therapy has demonstrated efficacy in HCC as both palliative therapy and bridge to “definitive therapy” such as transplantation by providing

locoregional disease control[2]. However, multiple factors affect objective TR to Y90 RE, including appropriate cytotoxic dose delivery to the targeted tumors[3, 4].

A direct dose-response relationship exists between delivered Y90 dose to the tumoral and normal non-tumoral liver (NTL), TR and hepatic toxicity[5-12]. Improvements in PFS and OS have been shown to occur in patients achieving objective TR across the majority of primary and metastatic liver tumors treated with Y90 RE[5, 6, 8, 9, 13-24]. These findings imply that the determination of tumor-specific dose response thresholds and optimization of tumor dose delivery while minimizing NTL dose will likely further improve post Y90 RE outcome.

However, reported TDR thresholds predicting objective TR vary widely, not only by malignancy type and grade, reflecting differential tumoral radiosensitivity, but also within the same tumor types and under similar conditions[17-19, 25]. Additionally, reported TDR thresholds in HCC for resin and glass microspheres are significantly different[7, 26]. Furthermore, both glass and resin Y90 microspheres demonstrate heterogeneity in distribution and absorbed radiation when delivered intra-arterially[27, 28]. Autoradiographic and pathologic analysis of patients with HCC treated with Y90 demonstrated a tendency for Y90 RE material to localize along the tumor periphery[27, 28]. Given that Y90 is a pure beta emitter with short tissue penetration of 2.5mm, absorbed radiation dose at the center of large tumors can be as low as 20 Gy, while the periphery of the tumor can receive >230 Gy[27-29]. Numerous factors are presumably responsible for such phenomenon, including tumor vascular density, flow dynamics, number of particles administered and clustering of particles. Of note, distribution of the particles and absorbed radiation is more homogenous in NTL compared to tumors, likely due to organized vasculature[27-29].

The above observations suggest that the use of mean absorbed dose for the entirety of the tumor is inaccurate for determining TDR because a single small area of microsphere concentration may spuriously suggest that a tumoricidal dose has been achieved. We believe that wide ranges in previously reported TDR thresholds are largely explainable by disparities in dosimetry methodology used by different investigators, the inadequacy of currently employed Y90 RE dosimetric techniques in addressing the complex interactions between the tumor microvasculature, RE devices (glass vs. resin) and resulting radioactive microsphere biodistribution[7, 30]. Other factors including the indirect and continuous Bremsstrahlung radiation spectrum detected on SPECT and alteration in flow biomechanics by surrogate injection may play secondary roles[7].

Manufacturer recommended Y90 RE dosimetry models include empiric (set dose of radiation delivered to liver lobe regardless of tumor type) and a variation of the body surface area method which can additionally factor in tumor volume as determined by cross-sectional imaging[31, 32]. Not only do these methods rely on variables that poorly correlate to absorbed dose prediction and Y90 microsphere biodistribution, they also fail to consider the highly unique tumor micro- and macro-environment. To date, the partition model is the most studied personalized dosimetry model, requiring the determination of MAA uptake TNR during the shunt study using

SPECT/CT[33]. In the partition model, MAA is assumed to mirror Y90 biodistribution and to distribute uniformly within the liver tumor and NTL, but at different concentrations. Such assumptions facilitate calculation of Y90 doses separately for the tumor and NTL which can be used to plan treatments based on dose limits that are thought to minimize pulmonary and hepatic toxicities[33, 34].

While the assumption of MAA mirroring the Y90 microsphere biodistribution has long been suspected to be inaccurate, only recently has its impact on dosimetry been quantified, with especially compelling data sourced from the current reference standard post-Y90 PET/CT, comparing the actual Y90 absorbed dose to that estimated from the MAA[19, 25, 27]. MAA has been shown to be an inaccurate estimator of LSF and Y90 biodistribution in the liver due to several factors, including size discrepancy between MAA and Y90 microspheres, as well as free pertechnetate overestimating LSF[35-37]. MAA consistently overpredicts LSF, sometimes by greater than 100%, and has a poor linear correlation with directly measured LSF using Y90 PET (correlation coefficient: 0.682)[25]. Conversely, MAA underpredicts TNR compared to that obtained on post Y90 SPECT and PET, with a wide range of linear coefficient ranging from 0.7-0.9[8, 25]. Furthermore, retrospective direct Y90 tumor dose measurement using PET and SPECT after Y90 therapy, while resource intensive, has limited clinical benefit, since patients are rarely retreated if “inadequate” dose is delivered to tumor[8, 25]. **Hence, there is a critical need to ensure the desired dose is estimated accurately in a prospective fashion prior to administration of the therapeutic Y90.**

These problems can be overcome by using a radioactive tracer in pre-treatment planning that is bioidentical to Y90 microspheres, which is the principle behind shunt study and treatment with Holmium-166 microspheres (¹⁶⁶Ho)[38]. Currently, ¹⁶⁶Ho is not available in the United States, and low-dose Y90 microspheres are the most readily available direct surrogate to predict LSF and tumor dose. Similar to the use of low-dose ¹⁶⁶Ho for treatment planning, a prospective personalized dosimetry method using direct yet non-toxic surrogate for therapeutic Y90 microspheres is necessary to further optimize Y90 dosimetry in a clinically pertinent manner. We believe that such efforts will not only standardize Y90 RE methodology and improve post Y90 RE outcomes under currently recommended indications but will also better allow accurate study of further indications. Additionally, LSF is a major determinant in the calculation of a safe Y90 dose as LSF > 20% is a relative contraindication to Y90 RE. Hence, it is possible that patients with inaccurately high LSF's estimated by MAA may receive lower suboptimal Y90 therapeutic doses or are entirely excluded from treatment, thus adversely impacting post-Y90 outcomes.

In summary, there is growing evidence that factoring individual patient characteristics into Y90 treatment planning are likely to significantly impact both TR and treatment tolerability. To this end, the partition model, while more resource intensive, has made great strides towards treatment individualization. However, the use of MAA in predicting post Y90 RE absorbed dose and

biodistribution is flawed and inaccurate, leading to suboptimal dose delivery, unnecessary hepatotoxicity and poor outcomes. **Therefore, we propose low-dose Y90 microspheres for therapy planning, as an alternative to MAA, to be a bioidentical therapeutic Y90 surrogate marker to better predict and thus achieve optimal therapeutic dosing.** Our long-term goal is to improve TR, PFS, and OS while reducing potential associated toxicities in patients treated with Y90 RE.

2.2.2 Correlative Studies Background

An anthropomorphic torso phantom with lung and liver compartments (Data Spectrum Corporation, Durham, North Carolina) was used to assess low-dose imaging capabilities with Y90 (**Figure 1**). Initially, 10.9 mCi of liquid Y90 HCL was injected into the liver compartment with an additional 2.9 mCi in two fillable spheres mounted in the liver to simulate liver tumors. Total liver activity was 13.8 mCi. Lung compartments were filled with a mixture of Styrofoam beads and a Y90 HCL solution with a total activity of 1.12 mCi. **This gave a true LSF of 7.5% and a TNR of 10.** The phantom was imaged using our planar imaging protocol for shunt calculations and with our SPECT/CT protocol for Y90. Energy windows were chosen for quantitative Y90 Bremsstrahlung imaging. Planar imaging (as clinically used for the MAA shunt studies) yielded 6.4% LSF. On the other hand, SPECT calculation of the lung shunt was 6.9%.

SPECT/CT depicted the distribution of activity in the phantom and gave TNR of 6. The PET/CT images on the other hand had very few counts in both the liver and lungs due to the small number of positron emissions by low-dose Y90. Nevertheless, the TNR measured by PET was very accurate at 10 and the LSF was measured at 4.9%. **As depicted by our phantom study results, each imaging modality in the setting of low-dose Y90 have advantages and disadvantages. While PET appears to be accurately measuring TNR, Bremsstrahlung SPECT appears to be more accurate in estimating LSF. Our goal through the proposed study is to ultimately optimize and validate low-dose Y90 PET and/or SPECT as the single study needed to accurately plan Y90 therapy based on institutional availability.**

[figure not shown]

Figure 1 shows images used in the phantom analysis: A) Planar (static image), B) SPECT coronal, C) CT coronal, D) PET coronal.

2.3 Potential Risks and Benefits

Potential Risks:

As with any Y90 radioembolization, the potential risks involved includes liver failure, non-target embolization resulting in stomach or duodenum/proximal jejunum inflammation or ulceration. Additionally, radiation induced lung disease is a potential risk of Y90 radioembolization. With accurate mapping and treatment planning, which is standard of care, the risk of either liver failure, non-target embolization or radiation induced lung disease are significantly less than 1%. Related to angiography, there is risk of vascular injury and bleeding either at the access site or at the celiac access or SMA (in case of replaced or accessory right hepatic artery). The risk of clinically significant vascular injury or bleeding requiring another intervention is less than 1%.

Additional angiographic and low dose CT scans of the PET/CT and SPECT/CT in this study also involve ionizing radiation with risk factors primarily related to increased chance of cancer

development in the future. However, given the amount of radiation involved, the risk of quite minimal. Of note, the study has already been approved by radiation safety committee at Emory.

Potential Benefits:

More accurate treatment planning with low-dose Y90 can result in maximizing dose delivery to the tumor while minimizing radiation dose to the non-tumoral liver and lungs.

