7.1.2 Dosing and Administration

Treatment will be administered on an *outpatient* basis. Reported adverse events and potential risks are described in Section 7. Appropriate dose modifications are described in Section 8. No investigational or commercial agents or therapies other than those described below may be administered with the intent to treat the patient's malignancy.

No dose escalation or dose expansion is planned in this procedure.

The treatment Y90 dose will be calculated using the partition model as detailed below:

The required therapeutic Y90 dose will be calculated using MAA SPECT, Y90 SPECT and Y90 PET. **Although all 3 sets of calculations will be made prospectively, the activity calculation based on MAA SPECT (the standard of care) will be used for actual treatment planning.** The activities calculated using Y90 SPECT and PET will be used for post-hoc analysis. Partition model to achieve cytotoxic Target Tumor Dose of >100 Gy will be utilized using the following formulas[7]:

- 1) **Desired Tumor Activity (GBq) = (100 Gy X Tumor Mass (Kg)) / 50**
- 2) **Targeted Normal Liver Activity (GBq) = Desired Tumor Activity (GBq) / TNR**
- 3) **Targeted Liver Lobe Activity (GBq) = (Targeted Normal Liver Activity + Desired Tumor Activity) (GBq)**
- 4) **Targeted Liver Lobe Dose (Gy) = Targeted Liver Dose Activity (GBq) X 50 / Liver mass (Kg)**

The liver and tumor mass will be determined using the volumes calculated by MIM software and assuming density of 1.03 g/cm³ [39]. It will be ensured that targeted liver dose remains below 50 Gy which has been shown to be safe with no sequela of radiation induced liver disease while ensuring the target tumor dose >100 Gy[7, 26].

5) Y90 Activity for administration (GBq) = Targeted Liver Lobe Activity (GBq) X (1+LSF)

Lung dose after therapeutic Y90 RE will be calculated using the following formula:

6) Lung Dose (Gy) = Y90 Activity to be Administered (GBq) X LSF X 50 / Mass of Lungs (Kg)

Lung Dose <30Gy will be ensured by reducing administered activity if needed (lung mass assumed at 1 Kg)[8].

The MAA, low-dose and therapeutic dose Y90 microspheres will be administered intra-arterially using the following technique:

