10. STATISTICAL CONSIDERATIONS

10.1 Study Design/Endpoints

Primary Objective Endpoints:

A) Accuracy/Efficacy: The accuracy/efficacy of MAA as a predictor of therapeutic Y90 distribution will be compared to that of low-dose Y90.

H₀: Y90 will have the same LSF as MAA.

H_A: Y90 will have significantly less LSF than MAA.

H₀: Y90 will have the same TNR as MAA.

H_A: Y90 will have significantly higher TNR than MAA.

B) Safety: adverse events related to Y90 radioembolization and angiography will be document by physical examination, clinical laboratory test and cross-sectional imaging.

No statistical consideration applied to the safety portion of the primary end point as it is a single arm study in which every patients undergo both mapping procedures with MAA and low-dose Y90. Detailed safety analysis plan is outlined below in section 10.5.

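### Under the protocol's own activity formulas, the hypothesised lower LSF and higher TNR mean less administered activity on average, so a positive primary result does not by itself support higher tumor dose or better dose prediction

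*Combined protocol and SAP*

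**What the plan says.** Section 2.3 gives as a potential benefit of low-dose Y90 planning "maximizing dose delivery to the tumor while minimizing radiation dose to the non-tumoral liver and lungs". Section 2.1 says that "patients with inaccurately high LSF's estimated by MAA may receive lower suboptimal Y90 therapeutic doses", or may be left untreated altogether. Section 4.2 blames MAA for suboptimal dose delivery and for avoidable liver toxicity.

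Section 7.1.2 (repeated in section 8.1, item G) fixes how a planning scan becomes an activity:
- Formula 1: "Desired Tumor Activity (GBq) = (100 Gy X Tumor Mass (Kg)) / 50".
- Formula 2: "Targeted Normal Liver Activity (GBq) = Desired Tumor Activity (GBq) / TNR".
- Formula 3 adds these two to give the lobe activity.
- Formula 5: "Y90 Activity for administration (GBq) = Targeted Liver Lobe Activity (GBq) X (1+LSF").
- Formula 6 gives lung dose as administered activity times LSF times 50, divided by lung mass (assumed 1 kg). Activity is reduced if needed to keep lung dose below 30 Gy, and the targeted liver dose is to stay below 50 Gy.

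Activities are calculated from MAA SPECT, Y90 SPECT and Y90 PET, but every patient is treated on the MAA SPECT figure.

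The alternatives in section 10.1 are that "Y90 will have significantly less LSF than MAA" and "Y90 will have significantly higher TNR than MAA". Section 10.3 tests them with paired t-tests of MAA against Y90. The Synopsis and section 4.1 also promise to compare the dose actually delivered to tumor, NTL and lungs with the dose each tracer predicted. Section 10 gives no analysis for that comparison.

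**The concern.** No patient is treated on a Y90-based plan, so any benefit has to be inferred through the activity formulas. On average these point away from the tumor half of the benefit statement: the hypothesised MAA errors (LSF too high, TNR too low) both raise the MAA-based activity.

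The planning tracer changes only one number, the administered activity. With the same injection site, the true split between compartments does not depend on which tracer was used to plan. Within one patient, changing tracer therefore cannot raise tumor dose while lowering NTL and lung dose.

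The primary tests also compare one tracer with the other, and neither with the post-therapy distribution. They can show that the tracers differ, but not which is closer to the delivered dose, which is what the primary objective asks.

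**Working it through.** **Check of the dose constant.** Section 4.3 states 27.8 Gy to the lungs from 15 mCi at LSF 100%. By formula 6, 15 mCi = 0.555 GBq, and 0.555 × 1 × 50 / 1 = 27.75 Gy. The figure reproduces.

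**Combined formula.** Let T be the desired tumor activity (formula 1: T = 2 × tumor mass in kg). Formulas 2, 3 and 5 give

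A = T × (1 + 1/TNR) × (1 + LSF).

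A rises with LSF and falls with TNR.

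**Inputs (section 10.2).** MAA: LSF 11.66%, TNR 5.4. Y90: LSF 50% lower, 5.83%. MAA TNR is 30% below Y90, so Y90 TNR = 5.4 / 0.7 = 7.71.

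**Activity at the means, no limit binding.**
- MAA: (1 + 1/5.4) × 1.1166 = 1.323, so A = 1.323 T.
- Y90: (1 + 1/7.71) × 1.0583 = 1.195, so A = 1.195 T.
- Ratio 0.903: 9.7% less on the Y90 plan. The LSF difference alone gives 0.948 and the TNR difference alone 0.953.

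**Delivered tumor dose if the Y90 values are true.** Dose = 100 × (A/T) × (1 − 0.0583) × 7.71/8.71.
- MAA plan: 110.3 Gy.
- Y90 plan: 99.7 Gy.

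NTL and lung dose are also constants times A, so they fall by the same 9.7%. For three spherical 7 cm lesions (0.555 kg at 1.03 g/cm³), lung dose goes from 4.28 to 3.87 Gy.

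**Other readings of TNR.** If Y90 TNR is 5.4 × 1.3 = 7.02, the fall is 8.6%. If TNR is a concentration ratio with an assumed NTL-to-tumor mass ratio of 2 to 10, it is 13% to 24%. The sign does not change.

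**Where a limit reverses the direction.**
- Lung limit: it binds when A × LSF exceeds 0.6 GBq. With three 7 cm lesions at LSF 20%, formula 6 gives 15.8 Gy at TNR 5.4 and 26.6 Gy at TNR 1, so it does not bind. At TNR 5.4 it binds from an LSF of about 34% (about 77% for one 7 cm lesion). At MAA LSF 50% and true LSF 25%, the three-lesion activity is 1.20 GBq on MAA and 1.57 GBq on Y90. True tumor dose then rises from 72 to 94 Gy and lung dose from 15.0 to 19.6 Gy.
- Liver limit: if it applies to formula 4's lobe dose, it cannot reverse the sign. The capped lobe activity on Y90 is no larger than on MAA, and it is then multiplied by a smaller (1 + LSF). A limit on NTL dose alone could reverse it.

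**Individual patients, no limit.** The hypotheses concern means. In a simulation with assumed lognormal LSF and TNR, the section 10.2 SDs for both tracers and within-patient correlation 0.5 (stated for LSF, assumed for TNR), the Y90-based activity is the higher one in about 7–8% of patients. Other SD choices give up to about 10%, and normal inputs about 15%. At correlation 0.9 the lognormal figure is 1% or less.

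**Lower LSF is not the same as more accurate LSF.** In the section 2.2.2 phantom the true LSF was 7.5%, and low-dose Y90 read 6.9% on SPECT and 4.9% on PET. The lowest reading was the furthest from the truth.

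**The case against.** - **A positive result does support part of the benefit.** At the assumed means, the Y90 plan lands close to the 100 Gy target with 9.7% less liver and lung dose. This stands. A reader might infer that a positive trial cannot support the stated benefit at all; the documents do not bear that out. What lacks support, on average, is the higher tumor dose.
- **The hypotheses are about means.** A reader might infer that every patient without a binding limit would get less activity on a Y90 plan. The assumed SDs and correlation contradict that, as the simulation shows.
- **Section 2.1 also describes exclusion from treatment**, just after calling LSF above 20% a relative contraindication. It is background on current practice, so it need not contradict formula 5. This stands. Under the section 10.2 mean and SD, about 14% (lognormal) to 21% (normal) of patients would have MAA LSF above 20%. However, patients who never receive therapy have no delivered dose to compare, so this trial cannot measure that benefit.
- **The liver limit could matter.** If TNR is a concentration ratio and 50 Gy applies to normal liver (both assumed), 100 Gy to tumor needs TNR of at least 2. A 30% under-reading by MAA would then wrongly restrict patients with true TNR from 2 to 2.86. This is a real but narrow exception.
- **The data for the right comparison are already planned**, and section 4.1 hypothesises more accurate prediction, not higher dose. This also stands. What is missing is the statistical specification in section 10.3.

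**Conclusion.** The point holds for mean values. If both hypothesised differences are real, the protocol's formulas give about 9.7% less activity on a Y90-based plan, and tumor, NTL and lung dose fall together by that factor (tumor about 110.3 to 99.7 Gy). A positive result on the two primary tests can support lower liver and lung dose at the price of a proportional fall in tumor dose. It does not by itself support higher tumor dose, and it does not show that low-dose Y90 predicts delivered dose better.

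This rests on the section 10.2 means, on the Y90 values being true, on the same injection site throughout, and on no limit binding. Exceptions are individual patients whose differences run the other way (about 7–8% under the stated simulation assumptions), patients in whom a limit binds, and patients excluded on a falsely high MAA LSF. The documents do not say that rejecting the nulls would show MAA under-doses tumors. Sections 2.1, 2.3 and 4.2 make that an easy inference, and the formulas do not support it on average.

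**What to change.** 1. Reconcile the benefit statements in sections 2.1, 2.3 and 4.2 with formulas 2 and 5. State the direction implied by the alternative hypotheses and the exceptions where a limit or exclusion applies. This changes no dosing rule.
2. In section 10.3, specify the comparison promised in the Synopsis and section 4.1. For each patient and each planning source (MAA SPECT, Y90 SPECT, Y90 PET), report the signed and absolute deviation of predicted from post-therapy delivered dose for tumor, NTL and lung. Compare sources in pairs with 95% CIs.
3. Add a paired comparison of the three prospectively calculated activities, and of the tumor, NTL and lung doses each would have given under the post-therapy distribution.
4. Rest any claim of better planning on smaller absolute deviation, not on lower LSF or higher TNR. Report separately the patients in whom a lung or liver limit bound.

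The cost is protocol wording and a short extra analysis of values already to be calculated, with no new patients or procedures. The benefit statement becomes less favourable.
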